8.2.2. Analysis of Secondary and Other Efficacy/Health Outcome Endpoints

Efficacy analysis will only include the data collected in the main LTE study.

Contingency/frequency tables as described in [Section 8.1.2](#) will summarize:

- ACR20, ACR50 and ACR70 response rate at all time points.

In addition, the ACR response rates will be displayed at all time points by the qualifying study. As a sensitivity analysis to using the baseline values from the qualifying study for all subjects, one will also provide tables of ACR response rates in which baseline is the baseline visit for A3921092 for patients whose enrollment are out of 14-day window.

- Psoriatic Arthritis Response Criteria (PsARC) response at all timepoints.
- Psoriasis Area and Severity Index 75 (PASI75) response, ie, the proportion of subjects achieving at least a 75% reduction in PASI relative to baseline for subjects with baseline BSA \geq 3% and baseline PASI $>$ 0 (see [Section 5.4.1](#)).
- Presence of dactylitis at all timepoints for subjects with baseline DSS $>$ 0.
- HAQ-DI response rates (2 endpoints: (decrease of \geq 0.30 and decrease of \geq 0.35) at all timepoints for subjects with baseline HAQ-DI \geq 0.30 and HAQ-DI \geq 0.35, respectively) (see [Section 5.4.1](#)).
- Minimal Disease Activity (MDA) at all timepoints.

Descriptive statistics as described in [Section 8.1.1](#) will be tabulated for:

- ACR response criteria components (Δ in HAQ-DI, CRP, Patient's Assessment of Arthritis Pain, Patient's Global Assessment of Arthritis, Physician's Global Assessment of Arthritis, swollen joint count, tender/painful joint count) at all timepoints.

In addition, the descriptive statistics for Δ HAQ-DI scores will be displayed at all timepoints by the qualifying study. As a sensitivity analysis to using the baseline values from the qualifying study for all subjects, one will also provide tables of

descriptive statistics in which baseline is the baseline visit for A3921092 for patients whose enrollment are out of 14-day window.

- *Physician's Global Assessment of Psoriasis (Δ PGA-PsO) response at all timepoints* for subjects with baseline PGA-PsO>0 (see [Section 5.4.1](#)).
- *PASI and PASI component scores (% Δ PASI and its clinical signs component scores)* at all timepoints for subjects with BSA \geq 3% and baseline PASI>0 (see [Section 5.4.1](#)).
- *BSA (% Δ BSA) at all timepoints* for subjects with baseline BSA>0 (see [Section 5.4.1](#)).
- *Dactylitis severity score (Δ DSS) at all timepoints* for subjects with baseline DSS>0 (see [Section 5.4.1](#)).
- *Enthesitis score (using Δ in Spondyloarthritis Research Consortium of Canada (SPARCC) Enthesitis Index and Leeds Enthesitis Index) at all timepoints* for subjects with baseline SPARCC Enthesitis Index>0 and LEI>0, respectively (see [Section 5.4.1](#)).
- *Bath Ankylosing Spondylitis Disease Activity Index (Δ BASDAI) at all timepoints.* Two analysis populations will be used: one for subjects with presence of spondylitis at screening and baseline BASDAI score>0 cm, and the other for subjects with presence of spondylitis at screening and baseline BASDAI score \geq 4 cm (see [Section 5.4.1](#)).
- Δ FACIT-F (3 endpoints: total score, experience score and impact score) at Month 1, Month 6 (and every 6 months thereafter).
- Δ in components and domains of the Short-Form-36 Health Survey (SF-36) Version 2, Acute at Month 1, Month 6 (and every 6 months thereafter); for each component and domain, only the scaled score should be analyzed (see [Appendix 2.17](#) for derivations).
- Health status and domains from the EuroQol 5-Dimension Health State Profile (Δ EQ-5D-3L and Δ EQ-VAS) at Month 1, Month 6 (and every 6 months thereafter).
- Δ in DAS28-3 (CRP) at all timepoints.
- Psoriatic Arthritis Joint Activity Index (raw PsAJAI), Disease Activity Index for Reactive Arthritis/PsA (Δ DAREA/DAPSA), Composite Psoriasis Disease Activity Index (Δ CPDAI), Psoriatic Arthritis Disease Activity Score (Δ PASDAS). Δ CPDAI will be summarized for subjects with baseline BSA \geq 3% (see [Section 5.4.1](#)).
- *Nail Psoriasis Severity Index (Δ NAPSI) Score at Month 1, Month 6 (and every 6 months thereafter)* for subjects with baseline NAPSI>0 (see [Section 5.4.1](#)).

- *Itch Severity Item (ΔISI) at Month 1, Month 6 (and every 6 months thereafter)* for subjects with baseline $ISI > 0$ (see [Section 5.4.1](#)).
- Patient's Global Joint and Skin Assessment ($\Delta PGJS$ -VAS) at all timepoints.
- Total score on the Ankylosing Spondylitis Quality of Life questionnaire ($\Delta ASQOL$) at all timepoints.
- Total score for the $\Delta DLQI$ and the four scale scores for ΔWLQ at Month 1, Month 6 (and every 6 months thereafter).
- PsA-HCRU (each of the scales) and Δ PsA-HCRU self-rating of job performance at work.

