3. STUDY DESIGN

This is a Phase 3, long-term, open-label extension study designed to evaluate the safety, tolerability and efficacy of tofacitinib in subjects with active PsA who have previously participated in randomized PsA clinical studies with tofacitinib. For subjects who complete participation in such a randomized clinical study with tofacitinib, the final visit of the qualifying study can be combined with the screening and baseline visit for this study. Additional assessments and inclusion/exclusion criteria are required for subjects who enroll >14 days after completing treatment in their qualifying study. In this case, a separate screening visit to determine subject eligibility is required followed by a baseline visit.

All eligible subjects from qualifying studies A3921091 and A3921125 will receive open-label tofacitinib 5 mg BID upon entry into A3921092. Subjects from A3921091 will receive first dose of study medication ≥ 1 week after last injection of study medication in that qualifying study. Tofacitinib dose may be increased to 10 mg BID at study visits if, based upon investigator's discretion, subjects receiving tofacitinib 5 mg BID would benefit from a higher dose and are not experiencing any tofacitinib-related adverse events, including abnormalities in laboratory parameters that are judged to be related to tofacitinib. Tofacitinib dose may be decreased (ie, 10 mg BID to 5 mg BID) for safety reasons at any time during the study. Treatment duration for subjects participating in the LTE study is approximately 3 years (36 standardized 4-week months). Subjects participating in the sub-study may have up to an additional 1 year (12 standardized 4-week months) of treatment for a maximum potential total of approximately 4 years (48 standardized 4-week months).

At various time points in this trial, safety measurements, including physical examination, clinical laboratory tests, adverse event monitoring, electrocardiograms (ECGs) and vital signs will be performed. All subjects will be monitored for clinical evidence of response of PsA to treatment. Health Outcome Measures (ie, Patient Reported Outcomes assessment questionnaires for pain, quality of life, physical function, fatigue, work limitations, health care resource utilization and health status) will also be performed at various time points in this trial. In addition, subjects will be monitored for serious infections, lymphadenopathy and lymphoproliferative disorder (LPD).

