9.3. Efficacy Analysis

The measures of efficacy will be summarized using descriptive statistics, such as number and percent, mean, standard deviation and quartiles at each visit where measured. Displays using stratification by participation in qualifying studies will also be included. Exploratory analyses may also be performed.

Complete details will be specified in the statistical analysis plan.

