Appendix 3. Prohibited Concomitant Medications

Subjects taking certain medications for PsA, and deriving inadequate benefit from them, may enter the study after a sufficient washout period for that medication. Subjects receiving certain medications for psoriasis may enter the study after a sufficient washout period for that medication ([Section 4.1.2](#), criterion #3).

All **biologic DMARDs** are prohibited and require a specific washout period (as listed in the protocol or based upon Sponsor review) prior to first dose of study treatment. Subjects on TNF inhibitors must discontinue according to the following criteria:

- Etanercept (Enbrel[®]): Discontinued at least 4 weeks prior to the first dose of study drug;
- Adalimumab (Humira[®]): Discontinued at least 10 weeks prior to first dose of study drug;
- Infliximab (Remicade[®]): Discontinued at least 8 weeks prior to the first dose of study drug;
- Golimumab (Simponi[®]): Discontinued at least 10 weeks prior to the first dose of study drug;
- Certoluzimab (Cimzia[®]): Discontinued at least 10 weeks prior to the first dose of study drug.

Patients entering from studies in which adalimumab (Humira[®]) was administered in a double-blind manner must have a minimum of 1 week washout after their last injection (placebo or adalimumab) and prior to their first dose of tofacitinib in this study.

Subjects receiving biologic agents for the treatment of psoriasis must discontinue according to the following criteria:

- Ustekinumab (Stelara[®]) must be discontinued for at least 12 weeks prior to first dose of study drug;
- Alefacept (Amevive[®]) must be discontinued for at least 8 weeks prior to first dose of study drug;
- Efalizumab (Raptiva[®]) is prohibited per exclusion criterion #12.

Other biologic agents used as DMARDs or used for the treatment of psoriasis are prohibited and require a 6 month washout period unless otherwise specified above.

The following traditional non-biologic DMARDs are prohibited: azathioprine, cyclosporine, mizoribin, tacrolimus and tetracycline (used as a DMARD). In the sub-study, sulfasalazine and leflunomide are considered prohibited medications.

All of these prohibited non-biologic DMARDs require a 4 week washout period prior to first dose of study drug.

Injectable (intravenous, intramuscular) corticosteroids are prohibited during the study ([Section 4.1.1](#)); intra-articular injections of corticosteroids are only permitted as rescue medication ([Appendix 6](#)).

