8.2. Statistical Analyses

Tofacitinib dose may be increased to 10 mg BID at study visits based upon investigator's discretion. Also, tofacitinib dose may be decreased (ie, 10 mg BID to 5 mg BID) for safety

reasons at any time. Hence changes in the dose are treatment related. Consequently, descriptive statistics will be displayed for just one treatment group: the entire cohort of subjects in which tofacitinib is dosed flexibly between 5 mg and 10 mg BID.

The baseline values for the safety endpoints come from the baseline of the qualifying study for patients who enroll within 14 days of the last visit of the qualifying study. For the patients whose enrollment are out of 14-day window, their baseline values of the safety endpoints will be from the baseline visit of this study, A3921092. The baseline values for all the efficacy or health-outcome endpoints come from the baseline of the qualifying study. In addition, as a sensitivity analysis for the ACR response rates and Δ HAQ-DI, the baseline value will be the baseline visit for A3921092 for patients whose enrollment is out of 14-day window.

All analyses will use FAS (Section 5.1) or FAS with some subjects excluded from analyses for certain endpoints (Section 5.4.1) except where indicated otherwise.

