8.3.2. Prior Drug Treatments for Psoriatic Arthritis

Prior drug treatment will include any treatment for PsA prior to the first dose of study medication in Study A3921092. It will include the drug treatment prior to the qualifying study, the treatment used during the qualifying study (which includes adalimumab but not tofacitinib) and any treatment used during the enrollment gap between the qualifying study and the Study A3921092.

- Prior DMARDs (disease-modifying antirheumatic drugs) drug treatment (yes, no), yes is defined for a subject who used any DMARDs;
- Prior bDMARDs (biologic DMARD) drug treatment (yes, no), yes is defined for a subject who used any bDMARDs;
- Prior TNFi (Tumor necrosis factors inhibitor) bDMARDs drug treatment (yes, no), yes is defined for a subject who used any TNFi bDMARDs;
- Prior non-TNFi bDMARDs drug treatment (yes, no), yes is defined for a subject who used any non-TNFi bDMARDs;
- Prior csDMARDs drug treatment (yes, no), yes is defined for a subject who used any csDMARDs;
- Prior non-DMARDs drug treatment (yes, no), yes is defined for a subject who used any non-DMARDs;
- Prior oral corticosteroids use (yes, no);
- Prior NSAIDs use (yes, no).

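### The LTE displays cannot separate subjects who came off blinded adalimumab from tofacitinib subjects within A3921091, so Month 1 results mix the two drugs to an unknown degree

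*SAP*

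**What the plan says.** SAP 8.2 explains that dose may move between 5 mg and 10 mg BID during the LTE for reasons related to treatment, and concludes that "descriptive statistics will be displayed for just one treatment group: the entire cohort of subjects". SAP 8.2.1 asks for laboratory summaries by treatment group and visit, but only that one group is defined.

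The planned splits in SAP 8.2.2 are two. For ACR: "In addition, the ACR response rates will be displayed at all time points by the qualifying study". For change in HAQ-DI, the "scores will be displayed at all timepoints by the qualifying study". Protocol 9.3 is worded more generally but uses the same stratifier: "Displays using stratification by participation in qualifying studies will also be included". Neither document plans an LTE efficacy or safety display by the treatment received in the qualifying study.

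On baseline, SAP 8.2 states: "The baseline values for all the efficacy or health-outcome endpoints come from the baseline of the qualifying study". For safety endpoints the same baseline applies to subjects who enrol within 14 days of the last qualifying visit. Later enrollees use the A3921092 baseline.

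On entry, Protocol section 3 states: "All eligible subjects from qualifying studies A3921091 and A3921125 will receive open-label tofacitinib 5 mg BID upon entry into A3921092". Protocol Appendix 3 adds that subjects from studies with blinded adalimumab "must have a minimum of 1 week washout after their last injection (placebo or adalimumab"). For other adalimumab users the same appendix requires at least 10 weeks.

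**The concern.** Entrants arrive from different treatments: tofacitinib 5 mg, tofacitinib 10 mg, placebo advanced at Month 3 to either dose (Protocol 1.2.2.3), and blinded adalimumab. All start the LTE at 5 mg BID. With a baseline that precedes the qualifying study, a Month 1 change can mean uninterrupted 5 mg, a dose halved at entry, or about four weeks of tofacitinib straight after a course of adalimumab. The tables cannot tell these apart.

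The split by study does not help where it is most needed. The study injections that Protocol section 3 mentions are in A3921091, and the abstract that the protocol cites for that study names adalimumab in its title. The adalimumab and tofacitinib arms therefore share one column. SAP 8.3.2 does recognise adalimumab given in the qualifying study as prior treatment, but only inside yes/no descriptive summaries and not as a stratifier of outcomes.

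At stake is what the early LTE response rates and laboratory changes can be attributed to. Change in laboratory values is part of a primary endpoint.

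**Working it through.** The LTE states no sample size, power or alpha for the plan to be checked against. Its size is set by rollover (Protocol 9.1). The check is therefore of timing, exposure and coverage.

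**Time since the last adalimumab injection.** Inputs: minimum gap 7 days and comparison washout 10 × 7 = 70 days (Protocol Appendix 3); target days and windows (SAP Appendix 1), where Day 1 is the first LTE dose. Days since injection = (study day − 1) + 7.

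- Month 1 target, Day 29: 28 + 7 = 35 days, or 5 weeks. Inside 70.
- End of the Month 1 reporting window, Day 57: 56 + 7 = 63 days. Inside 70.
- Month 3 target, Day 85: 84 + 7 = 91 days, or 13 weeks. Outside 70.
- Earliest Month 3 visit under the protocol's ±7 days, Day 78: 77 + 7 = 84 days. Outside 70.

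On this yardstick, one scheduled visit is affected out of 13 (Month 1, then Months 3 to 36 every three months).

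**Prior tofacitinib exposure at LTE entry**, for subjects who completed their qualifying study (12 months in A3921091, 6 in A3921125):

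- A3921091 tofacitinib arms: 12 months. Placebo-advanced: 12 − 3 = 9.
- A3921125 tofacitinib arms: 6 months. Placebo-advanced: 6 − 3 = 3.
- Adalimumab: 0.

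Those already on tofacitinib thus enter with about 3 to 12 months of it. LTE Month 36 means 36 months of tofacitinib for former adalimumab subjects and 12 + 36 = 48 for the A3921091 tofacitinib arms.

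**Does the sensitivity analysis cover this?** It re-baselines only subjects who enrolled more than 14 days after the qualifying study, and only for ACR response and change in HAQ-DI. A former adalimumab subject who rolls over directly keeps the earlier baseline in every planned table.

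**What pooling could hide (illustration on assumptions only).** Let s be the former adalimumab share, pA their Month 1 response rate and pT the rate in the rest. Pooled rate = s × pA + (1 − s) × pT. Assume pT = 0.60, s from 0.10 to 0.30 and pA from 0.30 to 0.70.

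- s = 0.30, pA = 0.30: 0.09 + 0.42 = 0.51, a shift of −9 points.
- s = 0.30, pA = 0.70: 0.21 + 0.42 = 0.63, a shift of +3 points.
- s = 0.10, pA = 0.30: 0.03 + 0.54 = 0.57, a shift of −3 points.
- s = 0.10, pA = 0.70: 0.07 + 0.54 = 0.61, a shift of +1 point.

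Even the direction depends on values that the documents do not give.

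**The case against.** The best defence is that this is a descriptive study of long-term safety with no hypotheses, that the overlap reaches one early visit, and that the A3921125 column appears free of study adalimumab, so the planned split already confines the problem to A3921091. All of that stands, and it limits the weight of the point. It does not remove it. SAP 8.2 justifies pooling by dose changes within the LTE, whereas the qualifying-study treatment was fixed before entry. The protocol's allowance for exploratory analyses commits the sponsor to nothing.

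Four stronger readings are tempting and should be resisted.

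- A reader might infer that Month 1 results in former adalimumab subjects are mostly adalimumab's. The documents do not show this. By then these subjects have had about four weeks of tofacitinib, Protocol 1.2.2.1 reports improvement in rheumatoid arthritis after as little as two weeks, and no adalimumab laboratory effects are given.
- A reader might infer that an early laboratory effect in new starters is diluted in proportion to their share. That requires no change in everyone else. Continuing subjects who enrolled within 14 days are also measured from a baseline before study tofacitinib, so their own tofacitinib change is in the pooled mean. Only a transient first-weeks effect would be diluted in that way, and the documents describe none.
- A reader might take the value at LTE entry as a clean pre-tofacitinib baseline. It was drawn on or soon after adalimumab, so change from it mixes withdrawal of one drug with the start of another.
- A reader might want the SAP Table 2 incidence rates split by every prior treatment. Those rates use no baseline, so the argument does not reach them, and the rarer adjudicated events would leave sparse cells.

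**Conclusion.** The point holds as a modest, inexpensive improvement to reporting. Within A3921091 the planned tables cannot separate former adalimumab subjects from tofacitinib subjects. For the former, Month 1 efficacy, and Month 1 laboratory change in those enrolling within 14 days, reflects adalimumab in part and to an unknown degree.

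This rests on three things: the minimum one-week gap, the use of the protocol's own 10-week washout as a yardstick for carry-over (not as a view on which washout is right), and the reading that the blinded adalimumab arm was in A3921091. Longer gaps would weaken it.

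The size cannot be computed, because the documents give neither the former adalimumab share nor response rates by arm. A reader might conclude that the whole LTE response curve is compromised. The timing supports that only for Month 1. Alpha, power and sample size are not affected.

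**What to change.** In SAP 8.2.2, display ACR response and change in HAQ-DI by last qualifying-study treatment. In SAP 8.2.1, do the same for key laboratory changes; the tests that Protocol 9.2.1 singles out would be a natural list. The minimum split is adalimumab versus tofacitinib. Preferably also separate 5 mg from 10 mg and identify placebo-advanced subjects, since those coming from 10 mg enter at half their previous dose.

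For former adalimumab subjects, add laboratory change from the last value before the first LTE dose, where that test was drawn, with a footnote that the value was taken on or soon after adalimumab. Availability needs checking test by test. Protocol 6.1.3 lists hematology, chemistry, CRP and urinalysis at a separate visit within 14 days, but no lipids or lymphocyte subsets. Protocol 6.1.2 refers combined-visit subjects to the qualifying study's end-of-study activities, which are not listed in these documents.

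Leave the Table 2 incidence rates pooled. The cost is extra tables and smaller cells, using values already collected.

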8.2.3. Analysis of Other Safety Data

Safety analysis will include cumulative data from both the main LTE study and sub-study.

- Vital signs and 12-lead ECG parameters will be summarized according to the PDS. This will include summaries with contingency tables (eg, normal, high, low), and descriptive statistics for change from baseline by visit.
- Demographic parameters will be summarized (as number and percent or mean, standard deviation, and range) by gender following the PDS.
- Clinical findings on any physical examination during the study, including investigator-reported clinically significant changes in physical examination from baseline (in this and/or prior study) during treatment, will be tabulated by following the PDS.
- Previous and concomitant medication usage by medication type will be tabulated using the WHO-Drug dictionary following the PDS.

To help better understand and interpret the observed safety results, registry databases will be utilized to construct an appropriate contemporaneous and/or historical control group. However, such an analysis is outside the scope of this SAP and will include data not only from this study but the data from the qualifying studies as well.

8.3. Baseline and Other Summaries and Analyses

8.3.1. Baseline Summaries

Baseline/screening will be the baseline/screening of the qualifying study. Baseline characteristics will include but may not be limited to the ones listed below and will be summarized descriptively. For continuous variables, the summary will include N, mean, SD and range; for binary and categorical variables, the summary will include frequencies and percentages. A missing category will be included for those subjects with missing value.

- Demographic characteristics:
 - Baseline age (2 categorizations: <18, 18-44, 45-64, ≥ 65 years; <18, 18-44, 45-64, 65-74, 75-84, ≥ 85 years; and continuous);
 - Sex (female, male);
 - Race (white, black, Asian, other);
 - Ethnicity (Hispanic/Latino, non-Hispanic/Latino);
 - Baseline body weight (<60, ≥ 60 to ≤ 100 , >100 kg; and continuous),
 - Baseline height (cm, continuous);
 - Baseline Body Mass Index (BMI: <18.5, 18.5 to <25, 25 to <30, 30 to <40, and ≥ 40 kg/m²; and continuous);
 - Geographic region (United States and Canada, Australia and Western Europe, Russia and Eastern Europe, Rest of World);
 - Screening smoking status (never smoked, ex-smoker, smoker);
 - Alcohol use [yes, no; continuous (units/week) for subjects who consumed any alcohol (responded Yes)].
- Baseline disease characteristics
 - PsA duration (<2, ≥ 2 years; and continuous);
 - Baseline PsA Subtype: (<5 joints, ≥ 5 joints) formed based on baseline swollen joint count (66) or baseline tender/painful joint count (68), ie, count any joint that is either swollen or tender/painful;
 - Baseline PASDAS: (≤ 3.2 , >3.2 to <5.4, ≥ 5.4 ; and continuous);
 - Baseline CPDAI (≤ 4 , >4 to <8, ≥ 8 ; and continuous) for subjects with baseline BSA $\geq 3\%$;
 - Baseline swollen joint count (66) (continuous);
 - Baseline tender/painful joint count (68) (continuous);
 - Baseline HAQ-DI (continuous);
 - Screening presence of distal interphalangeal joints involvement (yes, no);
 - Screening presence of arthritis mutilans (yes, no);

- Baseline presence of enthesitis measured by SPARCC enthesitis index or LEI (yes, no). Yes is defined for those subjects with baseline SPARCC enthesitis index >0 or LEI >0 ;
- Baseline presence of enthesitis measured by SPARCC enthesitis index (yes, no). Yes is defined for those subjects with baseline SPARCC enthesitis index >0 ;
- Baseline presence of enthesitis measured by LEI (yes, no). Yes is defined for those subjects with baseline LEI >0 ;
- Baseline enthesitis index measured by SPARCC enthesitis index (continuous) for those subjects with SPARCC enthesitis index >0 at baseline;
- Baseline enthesitis index measured by LEI (continuous) for those with LEI >0 at baseline;
- Baseline presence of dactylitis (yes, no). Yes is defined for those subjects with baseline DSS >0 ;
- Baseline DSS (continuous) for those subjects with DSS >0 at baseline;
- Baseline presence of spondylitis (yes, no). Yes is defined for those subjects with presence of spondylitis at screening and baseline BASDAI >0 ;
- Baseline BASDAI (0, >0 to <4 , ≥ 4) for those subjects with presence of spondylitis at screening. BASDAI score ≥ 4 indicates active disease/suboptimal treatment;
- Baseline BASDAI (continuous) for those subjects with presence of spondylitis at screening and BASDAI >0 at baseline;
- Baseline total psoriatic BSA (0, >0 to <3 , $\geq 3\%$);
- Baseline total psoriatic BSA (continuous) for those with BSA $>0\%$ at baseline;
- Baseline PASI (0, >0 to ≤ 20 , >20);
- Baseline PASI (continuous) for those subjects with BSA $\geq 3\%$ and PASI >0 at baseline;
- Baseline PGA-PsO (0, 1, 2, 3, 4);
- Baseline PGA-PsO (continuous) for those subjects with PGA-PsO >0 at baseline;
- Number (%) of subjects with baseline PGA-PsO ≥ 3 , PASI ≥ 12 and BSA $\geq 10\%$;
- Baseline SF-36v2 (8 domains, physical component score [PCS] and mental component score [MCS]);

- Baseline FACIT-F (FACIT-F total score, FACIT-F experience score and FACIT-F impact score);
- Baseline DLQI (<5 , ≥ 5 ; and continuous);
- Baseline CRP (≤ 2.87 , > 2.87 mg/L; and continuous);
- Baseline diabetes mellitus (yes, no) (see [Appendix 4](#) for definition);
- Baseline metabolic syndrome (yes, no) (see [Appendix 3](#) for definition);
- Baseline cardiovascular risks per PDS and detailed in the statistical programming plan;
- Baseline rheumatoid factor positive (yes, no);
- Baseline cyclic citrullinated peptide antibody positive (yes, no).

